8.10.1. Additional Post-Natal Follow-up

The Investigator will be asked to assist with collection of assessments of postnatal development as part of a separate protocol. Participation in that protocol is optional and will require that the subject review, agree and sign a separate informed consent document specific to that study, explaining the details of the post-partum follow-up for the subject and the newborn to participate in these assessments of postnatal development.

8.11. Occupational Exposure

An occupational exposure occurs when, during the performance of job duties, a person (whether a healthcare professional or otherwise) gets in unplanned direct contact with the product, which may or may not lead to the occurrence of an AE.

An occupational exposure is reported to the drug safety unit within 24 hours of the investigator's awareness, using the SAE report form, regardless of whether there is an associated AE/SAE. Since the information does not pertain to a subject enrolled in the study, the information is not reported on a CRF; however, a copy of the completed SAE report form is maintained in the investigator site file.

8.12. Withdrawal Due to Adverse Events (See Also the Section on [Subject Withdrawal/Early Termination](#))

Withdrawal due to AEs should be distinguished from withdrawal due to other causes, according to the definition of AE noted earlier, and recorded on the appropriate AE CRF page.

When a subject withdraws due to an SAE, the SAE must be reported in accordance with the reporting requirements defined below.

8.13. Eliciting Adverse Event Information

The investigator is to report all directly observed AEs and all AEs spontaneously reported by the study subject. In addition, each study subject will be questioned about AEs.

8.14. Reporting Requirements

Each AE is to be assessed to determine if it meets the criteria for SAEs. If an SAE occurs, expedited reporting will follow local and international regulations, as appropriate.

8.14.1. Serious Adverse Event Reporting Requirements

If an SAE occurs, Pfizer is to be notified within 24 hours of investigator awareness of the event.

In particular, if the SAE is fatal or life-threatening, notification to Pfizer must be made immediately, irrespective of the extent of available AE information. This time frame also applies to additional new information (follow-up) on previously forwarded SAE reports as well as to the initial and follow-up reporting of EDP, exposure via breastfeeding cases and occupational exposure cases.

In the rare event that the investigator does not become aware of the occurrence of an SAE immediately (eg, if an outpatient study subject initially seeks treatment elsewhere), the investigator is to report the event within 24 hours after learning of it and document the time of his/her first awareness of the AE.

For all SAEs, the investigator is obligated to pursue and provide information to Pfizer in accordance with the time frames for reporting specified above. In addition, an investigator may be requested by Pfizer to obtain specific additional follow-up information in an expedited fashion. This information collected for SAEs is more detailed than that captured on the AE CRF. In general, this will include a description of the AE in sufficient detail to allow for a complete medical assessment of the case and independent determination of possible causality. Information on other possible causes of the event, such as concomitant medications, vaccines and/or illnesses must be provided. In the case of a subject death, a summary of available autopsy findings must be submitted as soon as possible to Pfizer or its designated representative.

8.14.2. Non-Serious Adverse Event Reporting Requirements

All AEs will be reported on the AE page(s) of the CRF. It should be noted that the form for collection of SAE information is not the same as the AE CRF. Where the same data are collected, the forms must be completed in a consistent manner. For example, the same AE term should be used on both forms. AEs should be reported using concise medical terminology on the CRFs as well as on the form for collection of SAE information.

8.14.3. Sponsor's Reporting Requirements to Regulatory Authorities

Adverse event reporting, including suspected unexpected serious adverse reactions, will be carried out in accordance with applicable local regulations.

9. DATA ANALYSIS/STATISTICAL METHODS

Detailed methodology for the summary and descriptive analyses of the data collected in this study will be documented in a Statistical Analysis Plan, which will be maintained by the sponsor. This document may modify the plans outlined in the protocol; however, any major modifications of the planned analyses will also be reflected in a protocol amendment.

9.1. Sample Size Determination

This study is designed to collect information sufficient to describe the post-operative outcome of subjects who underwent a total knee, hip, or shoulder replacement while participating in tanezumab Study A4091056, A4091057 or A4091058 (treatment or safety follow-up period). In addition subjects with a qualifying total joint replacement after the last subject in the study completes the treatment period in Study A4091059, A4091061 or A4091063 may be included. The number of subjects who will enroll in this study is unknown but is estimated to be less than 250 subjects. Also unknown is the distribution of subjects across treatment groups (ie, the treatment given in Study A4091056, A4091057, A4091058, or other tanezumab study). Therefore, it is predicted that there will be insufficient statistical power to perform statistical inferential analyses. All analyses will be descriptive in nature.

9.2. Analysis of Endpoints

All subjects enrolled in the study who have a total joint replacement will be included in the summary tables.

A summary of data will be shown using subjects from study A4091058. The incidence of subjects with a total joint replacement will be summarized for all subjects, and split by Study A4091058 treatment group. These summaries will be shown as percentages, and for exposure-adjusted rates (using Study A4091058 treatment and follow-up period up to the time of surgery). Comparisons of the total joint replacement rates will be made between tanezumab versus active comparator treatment groups, using risk differences and ratios with 95% confidence intervals. Summaries of the time to total joint replacement surgery and time to first symptom (leading to total joint replacement surgery) will be summarized using Kaplan-Meier survival estimates from the date of first subcutaneous dose in Study A4091058, and shown overall, and split by Study A4091058 treatment group where there are sufficient numbers of subjects. A further summary of the incidence of subjects with total joint replacements will be shown separately for studies A4091056, A4091057, A4091059, A4091061 and A4091063, if applicable. Similar summaries by study will be shown for adjudication outcomes. The summary of time to total joint replacement surgery and time to first symptom (leading to total joint replacement surgery) will also be performed using data for subjects from Studies A4091056 and A4091057.

Unless otherwise stated, data from this study will be presented at Baseline and Weeks 4, 12, and 24 using observed data (no imputation for missing data), and at Week 24 using Last Observation Carried Forward (LOCF) for missing data. Data will be shown at the timepoints specified and also using change from (pre-surgery) Baseline when Baseline data are available and where relevant. Data will be shown overall, and split by treatment group. Data on surgical difficulty and outcomes, and subject safety data will be summarized by study, with an additional combined summary for the subjects from the osteoarthritis studies.

For the Surgeon's Assessment of Procedural Difficulty, the number and percentage of subjects in each category (Uneventful, Minor complications, Major complications) will be presented. Complications reported by the surgeon will be listed.

For the subject's overall satisfaction with surgery assessments (using the Self-Administered Patient Satisfaction scale, SAPS), the responses [score] for each category (Very Satisfied [100], Somewhat Satisfied [75], Somewhat Dissatisfied [50], Very Dissatisfied [25]) will be stratified by surgery type (hip, knee or shoulder) and summarized for each of the four items. The scale score is the unweighted mean of the scores from the individual items, ranging from 25 to 100 per item with higher scores indicating greater satisfaction. This total score will be stratified by surgery type (hip, knee or shoulder) and summarized. Responses to the question "How satisfied are you with the results of your surgery?" will also be stratified by surgery type (hip, knee or shoulder) and summarized as satisfied (very satisfied and somewhat satisfied categories combined) and dissatisfied (somewhat dissatisfied and very dissatisfied categories combined).

Similarly, the number and percentage of subjects who have required (i) additional or corrective procedures related to their total joint replacement and (ii) participating in physical rehabilitation activities related to their replaced joint will be presented. For these assessments, change from Baseline summary data are not relevant and will not be presented.

Average pain (NRS) in the replaced joint for all subjects, WOMAC Pain, Stiffness and Physical Function sub-scale scores for subjects who had total knee or hip replacement and SPADI Pain, Function and Total Score for subjects who had total shoulder replacement will be summarized (including change from Baseline summaries).

Adverse events and concomitant analgesic medications will be collected for each subject during the study according to the Schedule of Assessments. Standard safety reporting tables will summarize and list these safety data.

In addition, the number and percent of subjects with specified post-surgical complications will be presented. The list of post-surgical complications will be derived from reported adverse events and will consist of complications that are clinically significant and attributable to the total arthroplasty procedure eg, periprosthetic joint infection/wound infection, periprosthetic fracture, pulmonary embolism or sepsis/septicemia/shock. Literature reported analyses of post-surgical complications^{19,20} will be used for guidance in developing the list of post-surgical complications. The list of post-surgical complications will be developed during Study A4091064 and finalized prior to Study A4091058 database lock.

Separate adverse event summaries by parent study treatment group for adverse events of decreased sympathetic function will be presented.

For subjects from study A4091058 and for subjects from any of the osteoarthritis studies, summaries of total joint replacement, adjudication event rates and post-surgical outcomes will be shown for subgroups including age, gender, body-mass index (BMI), baseline Kellgren-Lawrence grade of the replaced joint (knees and hips only) and number of joints with OA.

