A summary of data will be shown using subjects from study A4091058. The incidence of subjects with a total joint replacement will be summarized for all subjects, and split by Study A4091058 treatment group. Comparisons of the total joint replacement rates will be made between tanezumab versus active comparator treatment groups, using risk differences and ratios with 95% confidence intervals. Summaries of the time to total joint replacement surgery and time to first symptom (leading to total joint replacement surgery) will be summarized using Kaplan-Meier survival estimates from the date of first subcutaneous dose in Study A4091058, and shown overall, and split by Study A4091058 treatment group where there are sufficient numbers of subjects. A further summary of the incidence of subjects with total joint replacements will be shown separately for studies A4091056, A4091057, A4091059, A4091061 and A4091063, as applicable. Similar summaries by study will be shown for adjudication outcomes. The summary of time to total joint replacement surgery and time to first symptom (leading to total joint replacement surgery) will also be performed using data for subjects from Studies A4091056 and A4091057.

Unless otherwise stated, data from this study will be presented at Baseline and Weeks 4, 12, and 24 using observed data (no imputation for missing data), and at Week 24 using Last Observation Carried Forward (LOCF) for missing data. Data will be shown at the timepoints specified and also using change from (pre-surgery) Baseline when Baseline data are available and where relevant. Data will be shown overall, and split by treatment group. Data on surgical difficulty and outcomes, and subject safety data will be summarized by study, with an additional combined summary for the subjects from the osteoarthritis studies.

For the Surgeon's Assessment of Procedural Difficulty, the number and percentage of subjects in each category (Uneventful, Minor complications, Major complications) will be presented. Complications reported by the surgeon will be listed.

For the subject's overall satisfaction with surgery assessments (using the Self-Administered Patient Satisfaction scale, SAPS), the responses [score] for each category will be stratified by surgery type (hip, knee or shoulder) and summarized for each of the four items. The total

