4.1. Inclusion Criteria

Subject eligibility should be reviewed and documented by an appropriate member of the investigator's study team before subjects are included in the study.

Appropriate members of the investigator's study team are the investigator or sub-investigator.

Subjects must meet all of the following inclusion criteria to be eligible for enrollment into the study:

1. Evidence of a personally signed and dated informed consent document indicating that the subject (or a legally acceptable representative) has been informed of all pertinent aspects of the study.

2. Subject has been randomized and treated with SC investigational product in tanezumab Study A4091056, A4091057, A4091058, A4091059, A4091061 or A4091063 and has completed the study or has been withdrawn from the study.
3. Actual or planned total knee, hip or shoulder replacement surgery during tanezumab Study A4091056, A4091057 or A4091058 **or** after the last subject in the study completes the treatment period in tanezumab Study A4091059, A4091061 or A4091063. Note: additional procedures in a subject undergoing total joint replacement surgery (eg, revision of a previously replaced joint in addition to a new total joint replacement) will be allowed, but subjects undergoing solely sub-total arthroplastic procedures (eg, hemi-arthroplasty) will not be eligible.
4. Subject is willing and able to comply with scheduled visits and other study procedures.

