At the Week 4, 12 and 24 post-surgery telephone contacts, subjects will be queried for rehabilitation activities related to the replaced joint. Specifically, subjects will be asked to respond yes or no to the following question:

- *Are you participating in physical rehabilitation activities related to your replaced joint?*

Subjects will be queried for details if the answer to the question is yes.

The data relating to the endpoints of physical rehabilitation, or additional or corrective procedure, related to the replaced joint up to Week 24 will be derived from an ongoing clinical review of the concomitant non-drug treatment/procedure case report form (CRF) page. This review will identify treatments that are relevant for these endpoints, and a log of such data will be maintained. The data relating to the endpoint of concomitant analgesic medication use will be derived from an ongoing review of the concomitant analgesic drug CRF page. These reviews will be made during the study and data will be finalized prior to the database release for this study.

Events identified as the first symptom leading to total joint replacement will be reviewed and determined prior to the unblinding for the respective parent study.

The list of post-surgical complications will be derived from reported adverse events and will consist of complications that are clinically significant and attributable to the total arthroplasty procedure eg, periprosthetic joint infection/wound infection, periprosthetic fracture, pulmonary embolism or sepsis/septicemia/shock. The list of post-surgical complications will be developed during Study A4091064 and finalized prior to Study A4091058 unblinding. Other adverse events may be identified as post-surgical complications after the unblinding of the Study A4091058 database. These events will also be summarized as complications, and will be noted as having been included in the list after the unblinding of the Study A4091058 database.

Adverse Events which are “treatment emergent” in relation to the Baseline study day will be reported overall and by prior study treatment group. Adverse events ongoing from the parent study will continue to be followed in this study. They will not be included in incidence tables from this study unless the severity worsens.

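### The protocol still plans Kaplan-Meier curves for a first symptom that counts as an event only if joint replacement follows, so an arm difference in symptom-to-surgery delay can look like a difference in onset

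*Protocol*

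**What the plan says.** Protocol 9.2, repeated in the synopsis, plans two Kaplan-Meier summaries from the first SC dose in A4091058: time to replacement surgery, and the one at issue, "time to first symptom (leading to total joint replacement surgery) will be summarized using Kaplan-Meier survival estimates from the date of first subcutaneous dose". They are to be shown overall and "split by Study A4091058 treatment group where there are sufficient numbers of subjects". The synopsis and Section 9.2 extend both to the two shorter osteoarthritis studies: "time to first symptom (leading to total joint replacement surgery) will also be performed using data for subjects from Studies A4091056 and A4091057".

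The documents do not fix the risk set for these curves. Section 9.2 opens with "All subjects enrolled in the study who have a total joint replacement will be included in the summary tables", which points to replaced subjects. The next analysis it describes points to everyone treated: "The incidence of subjects with a total joint replacement will be summarized for all subjects, and split by Study A4091058 treatment group". No censoring rule and no definition of a symptom is given. Qualifying surgery is defined in Protocol 4.1 as "Actual or planned total knee, hip or shoulder replacement surgery during tanezumab Study A4091056, A4091057 or A4091058", so a planned operation counts for entry.

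The SAP differs. Section 8.1 covers only continuous, categorical and binary summaries. The table in Section 8.2.2 has no time-to-event row and gives the method as None in every row. The only analysis set (Section 5.3) is enrolled subjects with a qualifying replacement. Section 6.1 nevertheless keeps the derivation: "Events identified as the first symptom leading to total joint replacement will be reviewed and determined prior to the unblinding for the respective parent study". Protocol Section 9 lets the SAP modify the protocol's plans but says that major modifications will also appear in a protocol amendment. Neither document says that the curve has been withdrawn.

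**The concern.** Kaplan-Meier estimation needs a subject's event status at time t to be known from what has happened by time t. Here the event is dated at symptom onset but becomes an event only through a later replacement. Two subjects with the same symptom in the same week are classified differently according to what happens afterwards, and the nearer the symptom lies to the end of follow-up, the less time there is for it to qualify.

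What is at stake is the by-arm reading. The protocol reports that tanezumab 5 and 10 mg had efficacy above NSAIDs (Section 1.2.3.1) and that the risk of rapidly progressive osteoarthritis exceeds that with active comparator (Section 1.2.3.2). Either could plausibly change the interval from symptom to surgery. If it did, the arms' curves would separate even with identical onset, in a study that forms part of the programme's joint-safety characterisation.

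**Working it through.** **The plan's own figures.** There is none to reproduce for this summary: no event rate, delay or power is stated. The only size figure is fewer than 250 enrolled, without derivation. Against the planned 690 + 810 + 3000 = 4500 osteoarthritis subjects, 250 is 5.6%.

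**Inputs from Protocol 1.2.3.1.** A4091058: 56 + 24 = 80 weeks and 1000 per arm. A4091056: 40 weeks. A4091057: 48 weeks.

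**Assumptions (not in the documents).** Constant onset hazard; exponential symptom-to-surgery delay with mean L weeks; no dropout; for the arm comparison, 8% of subjects with a surgery-bound onset by Week 80.

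**1. Share of onsets captured, surgery required by Week 80.** With onsets spread evenly over T = 80 weeks, the share is 1 − (L/T)(1 − e^(−T/L)).
- L = 12: 1 − 0.15 × 0.999 = 0.850
- L = 24: 1 − 0.30 × 0.964 = 0.711
- L = 36: 1 − 0.45 × 0.892 = 0.599

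**2. Onsets in Weeks 56–80 only** (T replaced by 24).
- L = 12: 1 − 0.5 × 0.865 = 0.568
- L = 24: 1 − 1 × 0.632 = 0.368
- L = 36: 1 − 1.5 × 0.487 = 0.270

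The loss is concentrated in late onsets.

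**3. Planned surgery counted.** If surgery up to a weeks after exit qualifies, the share is 1 − (L/80)(e^(−a/L) − e^(−(80+a)/L)). For a = 12 and L = 24: 1 − 0.30 × (0.607 − 0.022) = 0.825. A 24-week allowance under the 8% constant-hazard model gives about 98%, 90% and 80% at L = 12, 24 and 36. The loss shrinks but remains.

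**4. Same onset, different delay, all treated subjects at risk, surgery required by Week 80.** With λ = −ln(0.92)/80 = 0.001042, the apparent Week 80 incidence is 0.08 − [λ/(1/L − λ)](0.92 − e^(−80/L)).
- L = 12: 0.08 − 0.01267 × 0.9187 = 6.84%
- L = 24: 0.08 − 0.02566 × 0.8843 = 5.73%
- L = 36: 0.08 − 0.03899 × 0.8116 = 4.84%

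Delays of 12 versus 24 weeks give a spurious ratio of 1.19 (1.1 points); 12 versus 36 weeks give 1.41 (2.0 points). The slower-to-surgery arm appears to have fewer onsets. If every onset counted regardless of surgery, both arms would show 8.0%.

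**5. Same onset, replaced subjects only.** Nobody is censored and the curve runs to 100%. Median onset is 33.6, 30.1 and 28.2 weeks at L = 12, 24 and 36. The slower-to-surgery arm now appears to have earlier onset, so the direction is the reverse of step 4.

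**6. Shorter studies.** At L = 24 and the same hazard, capture is 52% over 40 weeks and 57% over 48 weeks, against 72% over 80 weeks. (The 71% in step 1 uses evenly spread onsets; the exact 8% hazard gives 72%.) Curves from the three osteoarthritis studies would therefore not be comparable with one another.

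**The case against.** The strongest reply is that the curve may never be produced: the SAP has no time-to-event output, and the protocol allows the SAP to modify its plans. That is largely right, and it makes the point mainly one about protocol text. But that text still stands, SAP 6.1 still derives the event, and the protocol promises an amendment for major changes.

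The second reply is that this is an untested, secondary description whose label discloses that the symptom led to surgery. This also stands. A reader might call it an endpoint, but it is in neither list of co-equal endpoints (Protocol 2.3, SAP 6.1). Disclosure of the conditioning does not stop a by-arm curve from being read as a comparison of onset.

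Three stronger readings are tempting and are not supported:
- *Late symptoms are counted as symptom-free.* This holds only if all treated subjects are at risk and censored at last follow-up, which neither document states for this curve. With replaced subjects only, such symptoms are left out and the bias reverses.
- *Surgery must fall within the study.* Planned surgery also qualifies, so the relevant delay may run to the decision to operate rather than to the operation.
- *Joints already symptomatic at entry would give zero or negative times.* Symptom is undefined. If first symptoms are taken from parent-study adverse events, Protocol 8.2 has those recorded from the first dose, so such times would not normally arise.

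Finally, the size rests on assumption. In step 4 the 1.1-point difference at 12 versus 24 weeks is about one standard error with 1000 per arm: √(0.0684 × 0.9316/1000 + 0.0573 × 0.9427/1000) = 1.1 points. It could not easily be told from noise, which is a further reason not to draw conclusions from the curve.

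**Conclusion.** The point holds as a defect in the protocol's planned summary, of moderate importance. Because the event is conditional on a later actual or planned replacement, the curve is distorted under either risk set, and the direction of any false arm difference depends on a choice that the documents leave open. Under constant onset, exponential delay and surgery required by Week 80, capture is about 85%, 71% and 60% at mean delays of 12, 24 and 36 weeks, and about 82% at 24 weeks if surgeries within 12 weeks of exit count.

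A reader might infer that the delay does differ between tanezumab and NSAID, or that a reported result is biased. The documents support neither: they give no delay in any arm, and the current SAP does not list the curve.

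**What to change.** Withdraw the first-symptom Kaplan-Meier summary from Protocol 9.2 and the synopsis, so that they agree with the SAP.

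If the first-symptom dates from the SAP 6.1 review are reported, give two by-arm descriptive summaries among replaced subjects: onset day relative to first SC dose, with any pre-dose onset as its own category, and the symptom-to-surgery interval. Label both as conditional on surgery and subject to truncation. This table has the same selection as a replaced-only curve; the label makes that visible but does not remove it. State that no between-arm conclusion on symptom onset will be drawn.

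Separately, reconcile whether time to replacement is still to be analysed by Kaplan-Meier. The protocol plans it and the SAP does not list it, so keeping it would mean adding an analysis to the SAP.

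Cost: a protocol wording change and, optionally, one small table from dates that the SAP 6.1 review should already supply. The loss is a cumulative symptom-onset curve, which this design cannot estimate without bias.
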